7. SAFETY

ICH requires that both investigators and sponsor follow specific procedures when notifying and reporting adverse events/reactions in clinical trials. These procedures are described in this section of the protocol.

7.1 Definitions

7.1.1 Adverse event Definition

An adverse event (AE) is defined as any untoward medical occurrence, in a patient or clinical trial subject treated by a medicinal product and which **does not necessarily have a causal relationship with this treatment**.

Intensity (severity):

Intensity of adverse events is assessed by the investigator. The intensity criterion should not be confused with the seriousness criterion, which is the guide for defining the reporting requirements.

The intensity of adverse events will be classified according to the NCI-CTCAE Version 5.0.

For any event not listed in this classification, the classification will be assessed as follows:

- **Mild** (grade 1): does not affect the patient's Activities of Daily Living (ADL)
- **Moderate** (grade 2): disrupts the patient's ADL
- **Severe** (grade 3): disabling; limiting self-care ADL
- **Life-threatening** (grade 4): urgent intervention indicated.
- **Death** (Grade 5)

Causal relationship to study drug/procedure:

Relationship between the AE and the study drug /procedure must be assessed following EVCTM (EudraVigilance Clinical Trial Module) criteria: reasonable possibility / no reasonable possibility. Important factors to be considered in assessing the relationship of the AE to study treatment include:

- The temporal sequence from drug/procedure administration
- Recovery on drug discontinuation (de-challenge), recurrence on drug re-introduction (re-challenge).
- Underlying, concomitant, intercurrent diseases.

7.1.2 Definition of serious adverse events

A serious adverse event (SAE) is an AE occurring during any study phase (i.e., screening, run-in, treatment, wash-out, follow-up), at any dose of the study drugs that fulfills one or more of the following criteria:

- **Results in death**
- **Is life-threatening**
- **Requires in-patient hospitalization or prolongation of existing hospitalization**
- **Results in persistent or significant disability or incapacity**
- **Is a congenital abnormality or birth defect in offspring of the patient**
- **Is an important medical event that may jeopardize the patient or may require medical intervention to prevent one of the outcomes listed above.**

The terms disability and incapacity correspond to any temporary or permanent physical or mental handicap that is clinically significant and affects the patient's physical activity and/or quality of life.

Hospitalisations already scheduled before the start of the trial are not considered a serious adverse event.

7.1.3 Expected adverse events

An Expected adverse event (EAE) is an effect already mentioned in the most current version of the applicable document used in this trial.

Reminder: Expected serious adverse events will be submitted by the sponsor to the competent authorities.

In PERTINENCE study, **we don't expect any ⁸⁹Zr-girentuximab adverse event** as it will be administered intravesically and rinsed out afterwards. It will not diffuse into the general circulation as with intravenous administration.

Clinical experience in 69 patients dosed with a **single intravenous administration** of ⁸⁹Zr-girentuximab exhibited that less than 10% of patients experienced a mild nausea, which was considered related to the study medication. Therefore, mild nausea is an expected side effect of girentuximab in case of single intravenous administration.

Expected adverse events related to intravesical administration are: mictorial burning, deposition or scaling in the urine, pollakiuria, fatigue, fever and haematuria. Patient will be informed to contact the investigator if one of these adverse events occurs.

7.1.4 Unexpected adverse events

An unexpected adverse event (UAE) is an event whose nature, severity, frequency, or course is not consistent with the information about the procedures and methods used in the trial, as defined in the Investigator's Brochure or trial documents.

Reminder: Suspected Unexpected Serious Adverse Reaction (SUSAR) should be reported without delay in the case of death or life-threatening events, or otherwise within 15 days of the sponsor's notification to the competent authorities.

For all SUSARs, the information of follow-up must be submitted in a new delay of 8 days to the Competent Authorities.

7.1.5 New Safety Issue

Any new data that may lead to a reassessment of the benefit/risk ratio of the trial, or that may be sufficiently important to consider changes in the conduct of the study, or trial-related documents, or that may lead to the suspension, termination or modification of the study protocol or similar trial.

7.2 Investigator obligations

7.2.1 Adverse Events reporting

Adverse Events will be recorded in the corresponding section of the e-CRF.

For this study, all adverse events occurred and medications taken should be recorded in the e-CRF **from the date of administration of ⁸⁹Zr- Girentuximab until 30 days after administration** regardless of whether they are related to ⁸⁹Zr- Girentuximab PET/CT.

7.2.2 Serious Adverse Events (SAEs) Reporting

7.2.2.1 Reporting information to Sponsor

Any expected or unexpected Serious Adverse Event (SAE) requires the completion of SAE form. The investigator must verify that the information provided on this form is accurate and clear (e.g., do not use abbreviations).

For each reported event, the investigator will complete the SAE Form with at least:

- The patient identification,
- The description of the event, as clearly as possible and in medical terminology,
- The intensity of the event,
- The start and end date of the event,
- The measures taken and whether or not corrective treatment is required,
- If the trial treatment has been interrupted,
- The evolution of the event. In case of a non-fatal event, the evolution have to be followed until the healing or the return to the previous state or the stabilization of possible after-effects,
- The causal relationship between this event and the treatment being tested or a research-related constraint,
- The causal relationship of the event with the treated pathology, another pathology or another treatment.
- The investigator should also attach to the SAE report, whenever possible :
 - ⇒ A copy of the hospitalization report or extension of hospitalization,

- ⇒ A copy of the autopsy report if necessary,
- ⇒ A copy of all additional test results performed, including any relevant negative results with the laboratory's normal values,
- ⇒ Any other document it deems useful and relevant.

All these documents must be anonymized.

All SAE will be followed by the investigator until complete resolution or stabilization (at a level acceptable to the investigator or return to the previous state) even if the patient is out of the trial. A final assessment will be sent to the sponsor.

7.2.2.2 SAE reporting procedure

All SAEs, whether or not related to the study drug/procedure (with the exception of those identified in the protocol as not requiring immediate reporting, see section 7.2.2.4), must be documented and reported to the Sponsor and the study vigilance contact (contact information below).

Completion and reporting procedure:

1. A SAE Form will be completed as precisely as possible, dated and signed by the investigator.
2. This SAE Form must be sent via e-mail to both e-mail addresses below:

[contact] AND [contact]

E-mail title should be completed as follows:

SAE_STUDY name_ddmmyyyy_site number-patient number_short SAE title with grade

The completed, signed and dated SAE Form should be attached to this e-mail (in pdf format)

3. An acknowledgment of receipt will be kept in the investigator study master file.

7.2.2.3 Notification to the sponsor

The investigator must **immediately (without delay)** and **no later than 24 hours** following knowledge of the event, notify the sponsor pharmacovigilance unit of **any SAE or any new issue** defined in sections 7.1.2 and 7.1.5:

- **From informed consent signature up to ⁸⁹Zr-girentuximab administration:** only SAE related to the study procedures must be reported to the sponsor.
- **From ⁸⁹Zr- girentuximab administration up to 30 days post-⁸⁹Zr- girentuximab administration:** all SAEs, whether or not related to the study drug/procedure, must be reported to the sponsor.

All delayed Serious Adverse Events (occurring after this period) considered reasonably related to ⁸⁹Zr- girentuximab must be reported without time limit.

Except those that are identified in the protocol as not requiring immediate reporting.

This initial SAE notification shall be followed promptly by a detailed written follow-up report(s) until event resolution.

7.2.2.4 Protocol specifications

Some events should not be considered as SAE.

In this protocol, the following events **are not to be considered as SAE**:

- All hospitalizations for medical or surgical treatment scheduled before study start.
- All hospitalizations for routine treatment or monitoring of the studied pathology not associated with a deterioration of the patient's condition.
- Admission for social or administrative reasons.
- Outpatient hospitalization,
- Progressions related to the disease under study.
- Deaths related to disease under study progression.

7.3 Sponsor obligations

7.3.1 SAE Analysis

The sponsor should assess:

- Causality of serious adverse events (all adverse events, for which there is a reasonable possibility that there is a causal relationship between the study drug/procedure and the event, should be qualified by the investigator or sponsor as reasonably suspected adverse events. If the assessment by the sponsor and the investigator are different, both opinions are mentioned in the report to the competent authority if required).
- The sponsor should qualify the SAE in suspected expected serious adverse reaction or in Suspected Unexpected Serious Adverse Reaction (SUSAR). The evaluation of expectedness is based on knowledge of the adverse reaction and the study drug/procedures. The sponsor should maintain detailed records of all serious adverse events reported by the investigators. These records will be forwarded to the National Health Authority (ANSM), upon request.

7.3.2 Relationship Scoring

In accordance with the ICH Recommendations on the Management of Adverse Events in Clinical Trials, ICH E2B(R3), version of May 12, 2005, a relationship assessment should be performed for any reported SAE.

EVCTM (EudraVigilance Clinical Trial Module) criteria should be used: reasonable possibility / no reasonable possibility.

7.3.3 Notification of SUSARs to competent authorities

The sponsor should report all Suspected Unexpected Serious Adverse Reaction (SUSAR) to the EMA (European Medicines Agency - Eudravigilance database), the French Health Authorities (ANSM), and the principal investigators.

In accordance with article R1123-53 of the Public Health Code, Suspected Unexpected Serious Adverse Reaction (SUSAR) should be reported to the competent authorities from the day the sponsor becomes aware of them:

- Without delay for death and life-threatening SUSAR,
- Until 15 calendar days for all other SUSAR.

Relevant additional Follow-up information regarding SUSARs should be reported to the EMA, ANSM and the investigators within eight days of the initial report.

7.3.4 Notification of New Safety Issue

The sponsor is responsible for alerting the principal investigator in case of identification of a New Safety Issue and should propose urgent measures to be implemented.

The sponsor is responsible for reporting to the competent authorities, **without delay**, any New Safety Issue and the proposed measures.

Relevant follow-up information regarding any New Safety Issue should be reported to the competent authorities within a new delay of 8 days.

7.3.5 Reporting of DSURs (Development Safety Update Report)

On the anniversary date of the Health Authorities trial authorization, the sponsor should report an Annual Safety Report (ASR) consisting of three parts:

- Part 1: Analysis of patient safety.
- Part 2: the list of all suspected serious adverse events (including unexpected serious adverse events) that occurred in the trial in France (and abroad, including in third countries) during the period covered by the report.
- Part 3: summary tables of all serious adverse events and serious adverse reactions that have occurred in the trial since the study start.

This report is sent to the competent authorities (ANSM), Ethics Committee (CPP) and principal investigators within 60 days of the anniversary date of the trial authorization.

7.3.6 Reporting of other safety data

The sponsor should report any safety data or new safety event to the competent authorities (ANSM and CPP) **as soon as possible and no later than 15 calendar days** from the first time the sponsor became aware of the minimum information for immediate reporting.

Relevant additional information must be transmitted within 8 days and 15 days new delay.

7.3.7 In utero exposure

If a patient becomes pregnant during the study, the pregnancy must be reported to the sponsor within a time frame defined by the sponsor.

The investigator informs the sponsor using a standard "Initial Pregnancy Data Collection" sheet. This form should include the expected date of delivery, the contact details of the obstetrician and of the planned maternity hospital if the pregnancy is ongoing.

In the case of the partner of a patient becomes pregnant, the pregnancy must also be reported to the sponsor in the same time frame. However, an authorization must be requested from the patient's partner in order to collect information about the pregnancy. This authorization must be kept in the patient's file.

The investigator should follow the patient until completion of the pregnancy and should notify the sponsor of the outcome using a standard pregnancy outcome form.

If the outcome of the pregnancy meets the criteria for immediate classification as an SAE (i.e., postpartum complication, spontaneous abortion, stillbirth, neonatal death, or congenital anomaly), the investigator should follow the procedures for reporting an SAE.

8. STATISTICAL METHODS AND SAMPLE SIZE DETERMINATION

8.1 Determination of sample size

As this study is an exploratory phase, 6 patients will be included in this study.

The limited sample size has been determined to take into account the fact that this study is a first-in-man intravesical procedure without intention to treat but necessary to confirm sufficient safety and utility for further patients.

This sample size was also used by Menke-van der Houven van Oordt et al (25) and should be able to reflect some inter-patients variability.

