This preclinical study was followed by a clinical pilot study in 12 patients refractory to standard treatment and planned to undergo a radical cystectomy (6). An intravesical instillation of an activity of 366 to 821 MBq (10 to 22 mCi) of the ^{213}Bi -anti-EGFR antibody was carried out in an empty bladder followed by 30 mL of PBS. Bladder was washed 120 min later. An excellent tolerability without any clinical or biological sign was observed in the 12 treated patients. Among the 12 treated patients, 3 who should have undergone a radical cystectomy, had a complete response which continued 3, 30 and 44 months after treatment.

These two preclinical and clinical studies showed the feasibility, absence of toxicity and efficacy of intravesical alpha-immunotherapy.

Intravesical instillation route has been chosen to limit the circulation of the radiopharmaceutical agent in the blood and to limit potential allergic immunoreactions with girentuximab which might occur by intravenous route.

The main objective of this study is to prove that the ^{89}Zr -Girentuximab is safe before developing a treatment for therapeutic purposes with girentuximab radiolabeled with a therapeutic radionuclide such as Astatine-211 (^{211}At -Girentuximab).

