1.4.2 Collective benefit

The extensive clinical experience with radiolabeled girentuximab has provided strong clinical evidence to support its use as a targeted PET imaging agent in clear-cell renal cell cancer.

CAIX, is a cell surface antigen expressed in 70% to 90% of bladder cancer NMIBC but not in normal urothelial tissue; therefore, it represents an optimal therapeutic target. There may be a role for CAIX as an intravesical target for instillation therapy(8).

Once ^{89}Zr -Girentuximab has been shown to be safe, we will develop a treatment of bladder cancer NMIBC for therapeutic purposes with girentuximab radiolabeled with a therapeutic radionuclide such as: $^{211}\text{Astatine}$.

Especially as local treatments such as mitomycin C and BCG therapy are in short supply worldwide, it is important to offer alternative treatments to postpone cystectomy.

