2. OBJECTIVES

2.1 Primary objective(s) and endpoint

2.1.1 Primary objective

The primary objective of this study is to assess the biodistribution of ^{89}Zr -girentuximab.

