8.4 Description of analysis sets

Data will be summarized by frequency and percentage for categorical variables and by median, range, IQR, or mean and standard deviation for continuous variables.

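### Sections 1.1 and 8.1 say the trial will prove or confirm safety, which six patients cannot do; the wording should match the descriptive pilot set out in Section 2

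*Combined protocol and SAP*

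**What the plan says.** Two places in the protocol make a safety claim in confirmatory terms.

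- Section 1.1: "The main objective of this study is to prove that the ^{89}Zr -Girentuximab is safe before developing a treatment for therapeutic purposes".
- Section 8.1, in the justification of the sample size: the study is "necessary to confirm sufficient safety and utility for further patients". No threshold for sufficient safety is given.

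The operative text is more modest.

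- Section 2.1.1: "The primary objective of this study is to assess the biodistribution of" the tracer. Safety and tolerability is the first secondary objective (2.2.1), measured as occurrence and frequency of adverse events to Day 30 (2.2.2). The monitoring plan in 9.2.2 lists the same endpoints in the same rank.
- Section 5.1 labels the study a feasibility pilot, uncontrolled and open-label. Section 8.1 opens with "As this study is an exploratory phase, 6 patients will be included in this study", and adds that a sample of this size "should be able to reflect some inter-patients variability".
- Section 8.4 is descriptive: "Data will be summarized by frequency and percentage for categorical variables", with medians or means for continuous variables. It mentions no confidence interval.

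Section 1.4.2 links safety to the next development step: once the product "has been shown to be safe, we will develop a treatment of bladder cancer NMIBC for therapeutic purposes". Section 6.5 contains the only numerical safety rule, given as an example of a reason to interrupt or end the study.

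**The concern.** To prove or confirm safety, a plan needs an event rate that would be unacceptable and enough patients to exclude it. Section 8 has neither. The product has not been given by this route before, and the programme it serves moves on to an alpha-emitting version of the antibody. The sponsor expects no product-related toxicity (1.4.4, 7.1.3), so a clean result in six patients is a likely outcome. Under 8.4 it would appear as a count and a percentage, with nothing to show how little it excludes. The wording in 1.1 also gives the study a main objective different from the one in 2.1.1.

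**Working it through.** **Inputs.** N = 6, single arm (5.1, 8.1). Safety endpoint: adverse events to Day 30 (2.2.2). Significance level, power, acceptable rate, margin and precision target: none stated. The true event rates used below are assumptions, shown as a range.

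**The plan's own figure.** No formula can reproduce N = 6. Section 8.1 rests it on the exploratory, first-in-man setting and on the same number having been used in a cited immuno-PET study. The check is therefore what six patients can show.

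**Upper limit after zero events (exact binomial, Clopper-Pearson).**

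- Two-sided 95%: 1 − 0.025^(1/6) = 45.9%
- One-sided 95%: 1 − 0.05^(1/6) = 39.3%

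With one event in six, the two-sided interval is 0.4% to 64.1%.

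**Chance of missing a reaction in all six patients, (1 − p)^6.**

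| Assumed true rate p | Missed in all six | Seen at least once |
|---|---|---|
| 5% | 73.5% | 26.5% |
| 10% | 53.1% | 46.9% |
| 20% | 26.2% | 73.8% |
| 30% | 11.8% | 88.2% |
| 40% | 4.7% | 95.3% |

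**Zero-event sample size, for scale.** Excluding a rate p at one-sided 95% needs n = ln(0.05)/ln(1 − p), rounded up: 9 patients for 30%, 14 for 20%, 29 for 10% and 59 for 5%.

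**Biodistribution.** The same binomial limits apply to its yes/no parts, namely positive blood radioactivity and visible spread on the whole-body scan. The bladder uptake and retained-activity endpoints are quantitative. If they are roughly normal, the 95% interval for a mean is ± t(0.975, 5)/√6 = 2.571/2.449 = ±1.05 SD. That figure does not apply to the medians and ranges that 8.4 also allows.

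**The rule in 6.5.** It is met by severe events in two patients out of three. It says when the study might be interrupted. Not meeting it is not a criterion for concluding safety.

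**The case against.** The strongest reply is that the protocol nowhere presents itself as confirmatory. It calls itself an exploratory feasibility pilot, Section 8.1 describes the sample as limited, and the phrase there can be read as enough reassurance to go on to further patients. The objectives and the monitoring plan are consistent with each other, and the sentence in 1.1 is one line of background. The safety case also draws on 69 patients given the product once intravenously (7.1.3) and on a 12-patient intravesical pilot with a different antibody and radionuclide (1.1, 1.4.4).

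Most of this stands, and it rules out several stronger readings.

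- A reader might infer that six patients is the wrong number. For a descriptive pilot it is not.
- A reader might infer that it is unclear which result decides the trial. Section 2 and 9.2.2 settle the ranking, and with no hypothesis test no single result formally decides it.
- A reader might infer that a clean result will be reported as proven safety. That is a prediction; no reporting text says so, and 8.4 would show the count alongside the percentage.
- A reader might infer that 1.4.2 starts the therapeutic programme on these six patients alone. The sentence is conditional and does not say that.

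The reply does not rescue the words themselves. Section 8.1 is the statistical section and leaves sufficient safety undefined. The earlier data concern another route or another product, so they do not narrow the interval for this product given intravesically.

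**Conclusion.** The point holds as a mismatch between wording and design, and it should be fixed. Sections 1.1 and 8.1 claim something six patients cannot deliver: a clean result would still be compatible with a true product-related event rate of up to 45.9% (two-sided) or 39.3% (one-sided), and a one-in-ten reaction would more often be missed than seen.

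These limits assume independent patients and a denominator of six. If a dosed patient is replaced under 3.5, the safety denominator grows and the limit moves little: 0/7 gives 1 − 0.025^(1/7) = 41.0%. The zero-event case matters mainly for product-related events and systemic spread, because 7.1.3 already expects some events from the instillation procedure. The documents do not support going further and calling the sample size or the ranking of endpoints defective.

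**What to change.** 1. **Section 1.1.** Replace the sentence on proving safety with the Section 2 objectives: biodistribution as primary, safety and tolerability as secondary.
2. **Section 8.1.** Replace the safety-and-utility claim with *a preliminary description of safety and biodistribution*, and add: *If no product-related event is seen in six patients, the exact upper 95% confidence limit for the true rate is 45.9% (two-sided) or 39.3% (one-sided).* Mark any ±1.05 SD statement for means as assuming normality.
3. **Section 8.4.** Report adverse event proportions, and the proportions with positive blood radioactivity and with whole-body spread, with exact 95% confidence intervals. List each patient's values for the quantitative endpoints.
4. **Section 1.4.2 (optional).** Refer to the absence of a safety signal in this pilot.

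The cost is wording in two sections, or three with the optional edit, and a short addition to the analysis. No patients, visits or procedures are added. The drawback for the sponsor is that the stated safety claim becomes less favourable.
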